6.7 Vaginal pH

Patients' vaginal pH will be assessed on Day 0 and on Day 7 by the Investigator or delegatee using a pH-test strip. Vaginal pH will be used for assessments of investigational product *in vivo* duration. If the vaginal pH on Day 7 is lower than the pH on Day 0, that would indicate appropriate release duration.

7 Method of Analysis

7.1 General

All statistical analyses will be performed in accordance with the ICH E9 guideline for Statistical Principles for Clinical Trials [1], using SAS® (Version 9.4 or higher, SAS Institute Inc., Cary, NC, USA).

7.1.1 Presentation of Results

All results will be presented by treatment group and in total, unless stated otherwise. It should be clearly stated which unit applies to each presented variable.

Continuous data will be summarised using descriptive statistics, and the following parameters will be reported:

- number of subjects with evaluable observations and missing observations
- arithmetic mean and standard deviation
- median
- first and third quartiles
- minimum and maximum.

Categorical data will be presented using absolute frequency and percentage. When the absolute frequency is zero, the percentage will not be presented.

Significance tests will be two-sided and performed at the 5% significance level, unless stated otherwise. When reporting the results of significance tests, p-values will be presented.

All confidence intervals presented will be two-sided with a nominal confidence level of 95%, unless stated otherwise.

Data will be presented using an appropriate number of decimal places, to ensure that undue precision is not implied (e.g. the number of decimals should not exceed the accuracy of the measuring instrument). Raw data will be presented with the same number of decimals as collected, and derived data with an appropriate number of decimals based on general practice, mathematical rationale or scientific rationale.

Minimum and maximum values will be presented with the same number of decimals as the analysed variable and the other descriptive statistics will be presented with one decimal more. Percentages and proportions will be presented with two significant digits. Confidence interval bounds will be presented with the same number of decimals as the corresponding point estimate, and p-values will be presented with 4 decimals or as '<.0001'.

Mock tables and graphs will be presented in a Data Display Plan (DDP), which will be a supplementary document to this analysis plan. The DDP will be finalised prior to database lock. Individual subject data listings will be presented according to the ICH E3 guideline for Structure and Content of Clinical Study Reports [2], unless stated otherwise.

Statistical Analysis Plan

Study ID: CL4

7.1.2 Baseline

Unless stated otherwise, the baseline value for a parameter is defined as the last non-missing value before the first administration of the investigational product. The start of the treatment period is explicitly defined as 18.00 at the day of screening.

7.1.3 Analysis Relative Day

The analysis relative day for an assessment/value is defined as the time in days from the first administration of the investigational product to the date of the assessment. The date of first administration of the investigational product is considered as Day 0, and earlier dates will correspond to a negative day.

7.1.4 Analysis Visit

An analysis visit is defined as a categorical variable used to classify values within an analysis variable into temporal or conceptual groups used for analyses.

The visits as defined in the case report form, CRF, will be used as analysis visits.

In general, data from unscheduled visits will be presented in data listings only and not included in analysis or summary tables. An exception to this is data used to confirm eligibility in association with screening or randomization where the last assessment will be considered in summaries of screening data.

7.1.5 Handling of Missing Data and outliers

In general, no imputation of missing data will be performed.

Sensitivity analyses to evaluate the effect of missing data for the primary endpoint is described in Section 7.9.2.

Data listings will include the observed values. Outliers will generally be included in all analyses. However, individual values might be excluded based on scientific decisions taken at clean file.

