12.4.2 Primary endpoint analysis

In the estimand setting, the primary endpoint will, in addition to the definition stated in [Section 4.1.1](#), take the following identified intercurrent events into account:

1. Concomitant anti-fungal therapy or other treatments related to VVC due to lack of clinical performance prior to CVVS evaluation used for the primary endpoint definition.
2. Treatment discontinuation due to lack of clinical performance.
3. Rescue medication prior to the CVVS evaluation used for the primary endpoint definition.

Applying the composite strategy to account for these intercurrent events, these have been incorporated in the endpoint definition. Thus, to be defined as clinically cured on Day 7-14, the patient needs to have the last available CVVS score equal to or below 3 at Day 7-14, and that none of the above stated intercurrent events have occurred. If the CVVS score is above 3, or any of the intercurrent events has occurred, the patient is defined as not clinically cured on Day 7-14.

Patients with missing CVVS score at Day 7-14 and no intercurrent events will be considered as missing in the analysis.

The primary endpoint clinical cure rate on Day 7-14, as defined in the section will be calculated and presented together with a one-sided 95 % CI based on the Wilson score.

The primary performance objective of the trial is to show that the clinical cure rate is above 30 %, i.e. to show that the lower limit of the one-sided 95 % CI for the observed cure rate is above 30 %.

Hypotheses for the primary clinical performance endpoint

Null hypothesis: Clinical cure rate is less than or equal to 30 %.

Alternative hypothesis (one-sided): Clinical cure rate is above 30 %.

Sensitivity analyses to evaluate the effect of missing data for any of the 6 individual vulvovaginal signs and symptoms scores included in the CVVS score will be performed. Details on the sensitivity analyses will be described in the SAP.

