7.9.2 Primary Variable

The primary endpoint is the clinical cure rate on Day 7-14, which is defined as the percentage of patients clinically cured at Day 7 to Day 14.

Clinical cure is defined as the absence of signs and symptoms of VVC in terms of having a CVVS score ≤ 3 .

Each of the following 6 vulvovaginal signs and symptoms will be individually scored using the scoring scale below.

- Vulvovaginal signs: erythema, oedema and excoriation
- Vulvovaginal symptoms: itching, burning and irritation

Scoring scale: each score should be objectively defined:

- 0 = none (absent)
- 1 = mild (slight)
- 2 = moderate (definitely present)

Study ID: CL4

3 = severe (marked, intense)

The CVVS score is the sum of the 6 individual scores. If any of the 6 individual signs and symptoms are missing, then the CVVS score will be considered missing. The last non-missing assessment of CVVS in the interval of Day 7-14 will be used. However, if the patient received rescue medication between the CVVS assessments at Day 7 and 14, CVVS data from Day 7 will be used. The same derivation will be made for secondary and exploratory endpoints made during the same time interval Day 7-14.

In the estimand setting, the primary endpoint will take the following identified intercurrent events into account:

1. Concomitant anti-fungal therapy or other treatments related to VVC due to lack of clinical performance prior to CVVS evaluation used for the primary endpoint definition.
2. Treatment discontinuation due to lack of clinical performance.
3. Rescue medication prior to the CVVS evaluation used for the primary endpoint definition.

Rescue medication prior to the CVVS evaluation used for the primary endpoint definition. From a practical perspective, bullet points 1 and 3 above will be regarded as the same in this study. Applying the composite strategy to account for these intercurrent events, these have been incorporated in the endpoint definition. Thus, to be defined as clinically cured on Day 7-14, the patient needs to have the last available CVVS score equal to or below 3 at Day 7-14, and that none of the above stated intercurrent events have occurred. If the CVVS score is above 3, or any of the intercurrent events has occurred, the patient is defined as not clinically cured on Day 7-14.

Patients with missing CVVS score at Day 7-14 and no intercurrent events will be considered as missing in the analysis.

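### The missing-data sensitivity analyses that SAP 7.1.5 places in 7.9.2, and that the protocol defers to the SAP, are not written there, and the complete-score rule leaves some certain non-cures coded as missing

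*SAP*

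**What the plan says.** SAP 7.1.5 sets the general rule, "In general, no imputation of missing data will be performed", and then refers the reader on: "Sensitivity analyses to evaluate the effect of missing data for the primary endpoint is described in Section 7.9.2".

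Protocol 12.4.2 makes a more specific commitment. It announces "Sensitivity analyses to evaluate the effect of missing data for any of the 6 individual vulvovaginal signs and symptoms scores" and adds "Details on the sensitivity analyses will be described in the SAP".

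SAP 7.9.2 defines how missing scores are handled in the primary analysis:

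- Item level: "If any of the 6 individual signs and symptoms are missing, then the CVVS score will be considered missing". Protocol 4.1.1 has the same rule.
- Visit level: "The last non-missing assessment of CVVS in the interval of Day 7-14 will be used". If rescue was given between the two visits, the Day 7 score is used.
- Patient level: "Patients with missing CVVS score at Day 7-14 and no intercurrent events will be considered as missing in the analysis".
- Other endpoints: "The same derivation will be made for secondary and exploratory endpoints made during the same time interval Day 7-14".

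The rest of 7.9.2 gives the scoring scale, the intercurrent events, the Wilson interval and the hypotheses. It contains no sensitivity analysis. None appears elsewhere in 7.9, and 7.10 does not list one as dropped.

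**The concern.** The trial's conclusion rests on one proportion compared with a fixed 30% in about 24 to 26 women, so a change of one or two patients can decide it. Both documents recognise that missing data need a sensitivity analysis, and neither specifies one.

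The item-level analysis is the important omission. Each item is scored 0 to 3, so a missing item can only add to the total. A woman whose observed items already sum to 4 or more cannot be a cure, yet her score at that visit is coded as missing. If she has no complete score at the other visit and no intercurrent event, she is coded missing and a known failure is lost.

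In one narrow case she is counted as cured. This requires a Day 7 clinical cure without mycological cure, no rescue, and an incomplete Day 14 score that is already at least 4. The last-non-missing rule then reaches back to the Day 7 cure. Other Day 7 cures have no Day 14 visit (protocol 5.4.3 and 5.4.5).

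**Working it through.** **Inputs.** Null rate 30%, one-sided 95% Wilson lower limit that must exceed 30% (SAP 7.9.2). Assumed true rate 54%, 24 evaluable, 26 enrolled (SAP 5.1). Prior-study rate 41% (protocol 12.6). The only missing-data figure in the documents is 26 against 24, that is 2/26 = 7.7%.

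**The plan's own figure.** n = [(1.645·√(0.30·0.70) + 0.842·√(0.54·0.46)) / 0.24]² = [(0.754 + 0.419)/0.24]² = 23.9, rounded up to 24. The sample size reproduces and is not in dispute.

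**Wilson lower limit.** With p = x/n and z = 1.645:

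L = [p + z²/2n − z·√(p(1−p)/n + z²/4n²)] / (1 + z²/n)

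For 11/24: (0.4583 + 0.0564 − 0.1765)/1.1127 = 0.304.

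| Cures / n | Lower limit | Result |
|---|---|---|
| 11/24 | 30.4% | pass |
| 11/25 | 29.1% | fail |
| 11/26 | 27.8% | fail |
| 12/25 | 32.6% | pass |
| 12/26 | 31.2% | pass |

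With two missing and 11 observed cures, leaving the missing women out gives success, and counting both as uncured gives failure. With one missing, both conventions need 12 cures, so the choice has no effect.

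**Chance that the convention decides the result.** Exact enumeration over the number cured and the numbers missing among cured and uncured women, with 26 treated. The missing rates are assumptions.

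| Missing pattern | Complete-case success at true 30% | Conclusions differ at true 30% / 41% / 54% |
|---|---|---|
| None | 6.0% | none |
| 7.7% regardless of outcome | 5.7% | 2.3% / 8.7% / 8.8% |
| 7.7% of uncured only | 8.2% | 2.2% / 5.1% / 2.5% |
| 7.7% of cured only | 3.8% | 0.4% / 2.5% / 4.2% |

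Every difference has the same form: complete-case succeeds and missing = not cured fails. That alone does not make the complete-case result wrong.

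**Item rule.** If the observed items sum to s and k items are missing, the true total lies between s and s + 3k. So s ≥ 4 is a certain non-cure, s + 3k ≤ 3 is a certain cure, and anything else is undetermined. With one item missing there are 4⁵ = 1,024 possible patterns of the other five: 968 are certain non-cures, 1 (all zeros) is a certain cure and 55 are undetermined. These are counts of patterns, not probabilities for patients.

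**The case against.** Much of the case on the other side stands.

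- **Denominator.** A reader might infer that it is left open, because the main analysis is on all treated women. The documents do not support that. Coding women as missing, the no-imputation rule and the enrolment of 26 to yield 24 all point to treated women with a non-missing outcome. One explicit sentence is all that is needed.
- **Inflated false-success rate.** A reader might infer that missing data substantially raise the chance of success at a true 30%. A figure of 14.1% can be produced, but only if 20% of uncured women and no cured women are missing. That averages 3.6 missing women (0.20 × 0.70 × 26) against the planned two, in a pattern the design limits. Rescue, other VVC treatment, and discontinuation for lack of performance count as not cured. Women uncured at Day 7 who do not start rescue have a second visit.
- **Item rule.** The same definition stands in both documents, and the promised item-level analysis is what would address its weakness. The eCRF checks and query process (protocol 11.1) should make partly missing scores uncommon.
- **Withdrawal data.** A reader might infer that questionnaire symptoms from a missed visit routinely create partial scores. SAP 6.4 has the investigator ask about and record symptoms on Days 0, 7 and 14. SAP 7.1.4 uses the CRF visits for analysis and in general only lists unscheduled data. Neither section names the early-withdrawal visit, so a clarification is still reasonable.
- **Unseen tables.** A separate Data Display Plan holds the mock tables and is not available. It would not make the pointer to 7.9.2 correct.

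None of this answers the main point: the promised analyses are not where the SAP says they are.

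**Conclusion.** The cross-reference leads to nothing and the protocol's commitment is unmet. That is visible on the page and needs no assumption. The gap matters because a stated rule can code a known failure as missing and, in the narrow Day 7 case, count it as a cure.

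The size of the effect is much less certain, because the documents give no rate of partly missing scores. With the planned two women missing, the handling convention decides the result only at exactly 11 observed cures. At 7.7% missing regardless of outcome it does so with probability 2.3% to 8.8% over the true rates considered. Complete-case success at a true 30% lies between 3.8% and 8.2% over the 7.7% scenarios, against 6.0% with none missing. The direction of any bias depends on who is missing, which the documents do not tell.

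This should be fixed. It does not invalidate the primary test, but as the SAP stands there is no specified way to show that the result does not depend on missing data.

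**What to change.** In SAP 7.9.2, so that the pointer in 7.1.5 becomes true:

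1. Write the item-level sensitivity analysis that the protocol promises. At each visit, before visit selection: observed sum of 4 or more = not cured; observed sum plus 3 × number of missing items of 3 or less = cured; otherwise missing. State that the numeric change in CVVS keeps the complete-score rule, as an exception to "The same derivation will be made for secondary and exploratory endpoints made during the same time interval Day 7-14".
2. Add a supportive analysis on all FAS women with missing = not cured, reporting the Wilson lower limit. The documents do not name this method; it is a proposal. It is conservative: at a true 54% with 7.7% missing regardless of outcome, the chance of success is 71.6% against 80.4% for complete-case. It should therefore not replace the primary analysis.
3. Add one sentence that the primary denominator is FAS women with a non-missing outcome. Add one on whether withdrawal-visit scores can enter the Day 7-14 CVVS, consistent with SAP 6.4 and 7.1.4.

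Keep the primary rule unchanged unless it is amended before the data are examined; SAP section 2 asks for a protocol amendment if a principal feature changes. The study is open-label, the last visit was planned for 2023, and SAP v2.0 was signed in March 2024; the lock date is not given. The additions should be dated, and reported as post hoc if the data have been seen.

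The cost is SAP text, one derivation and one or two supportive tables. No new data are needed.

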7.1.6 Interim Analyses

Not applicable, no interim analyses will be performed.

7.1.7 Multiplicity

There is only one primary variable and therefore no adjustment for multiple comparisons were made.

For the secondary variables, no adjustments for multiple comparisons were made; it should be noted that the probability of making a type I error increases with the number of statistical tests performed.

7.1.8 Subgroups

Two subgroup analyses will be performed descriptively. Clinical cure as defined in the primary endpoint will be summarized stratified by site and the number of previous infections. The latter will be grouped as 0-1 infections, 2 infections or 3 infections. A Wilson score CI will be presented for the proportion of clinical cure stratified by number of infections.

7.2 Analysis Sets

The decision on the classification of subjects to each analysis set will be taken at the clean file meeting, prior to locking the database, and documented in the clean file report together with the reasons for excluding subjects from analysis sets.

7.2.1 Full Analysis Set

The full analysis set (FAS) is defined as all subjects who received at least one administration of the investigational product.

7.2.2 Per Protocol Analysis Set

The per protocol analysis set (PPAS) is defined as the subset of subjects in the full analysis set for whom no protocol deviation judged as having an impact on the primary efficacy analysis was reported or identified.

Statistical Analysis Plan

Study ID: CL4

The decision as to which protocol deviations should be considered as reason for exclusion from the per protocol analysis set should be made at the clean file meeting and documented in the clean file report.

7.2.3 Day 25 Per Protocol Analysis Set

The day 25 per protocol analysis set (PPAS25) is defined as the subset of subjects in the FAS for whom no protocol deviation judged as having an impact on the day 25 analyses was reported or identified.

The decision as to which protocol deviations should be considered as reason for exclusion from the PPAS25 should be made at the clean file meeting and documented in the clean file report.

7.3 Disposition of Subjects

The following will be presented:

- Number of screened subjects
- Number of screening failures
- Number of enrolled subjects
- Number of subjects who received at least one administration of the investigational product.
- Number of subjects who completed the study.
- Number of subjects who withdrew prematurely from the study.
- Number of subjects in each of the analysis sets.

In addition, the primary reason for premature withdrawal from the study will be presented.

The number of subjects attending each study visit will also be summarised.

7.4 Protocol Deviations

Protocol deviations will be presented in a data listing.

7.5 Demographics and Baseline Characteristics

Summary statistics and frequencies on demographic data (age, sex and ethnic origin) and consent details (childbearing potential, number of VVC infections during last 12 months) will be presented for the FAS.

7.6 Medical History and Concurrent Diseases

Medical history and concurrent diseases will be coded according to the Medical Dictionary for Regulatory Activities (MedDRA).

For each system organ class and preferred term, the number and percentage of subjects with at least one condition in that system organ class or preferred term will be presented. Medical history and concurrent diseases will be presented based on the full analysis set.

Medical history is defined as events stopped prior to baseline. Concurrent diseases are defined as ongoing events and events stopped on or after baseline. If the start and/or stop date is partially unknown, the following imputation rules will be used for the purpose of classifying the events:

	Imputed start date	Imputed end date
Unknown year	Missing	Missing
Unknown month	1 January	31 December
Unknown day	First of month	Last of month

If it is not possible to classify the condition based on the reported and/or imputed start and end dates, it will be considered as concurrent. In data listings, the dates will be presented as reported.

7.7 Prior and Concomitant Medication

Medications will be coded according to the ATC classification system' (ATC/DDD Index 2022) and summarized by therapeutic subgroup (ATC level 2) and chemical substance (ATC level 5).

Statistical Analysis Plan

Study ID: CL4

For each therapeutic subgroup and chemical substance, the number and percentage of subjects who used at least one medication of that therapeutic subgroup or chemical substance will be presented. Prior and concomitant medications will be summarized in separate tables, based on the full analysis set.

Prior medication is defined as medication stopped prior to baseline. Concomitant medication is defined as ongoing medication or medication stopped on or after baseline. If the start and/or stop date is partially unknown, the following imputation rules will be used for the purpose of classifying the medication:

	Imputed start date	Imputed end date
Unknown year	Missing	Missing
Unknown month	1 January	31 December
Unknown day	First of month	Last of month

If it is not possible to classify a medication based on the reported and/or imputed start and end dates, it will be considered as concomitant. In data listings, the dates will be presented as reported.

7.8 Compliance

Compliance will be calculated as specified in Section 8.3. Compliance will be summarised for the full analysis set.

7.9 Efficacy Evaluation

All endpoints, clinical performance and safety, will be performed on the FAS and will be considered as the main analyses. Supportive analyses for clinical performance will be performed on the PPAS for all efficacy endpoints, except Day 25 assessments, which will be performed on PPAS25.

7.9.1 Estimand consideration

The study estimands will be defined based on the 5 attributes listed in the ICH E9 (R1) guideline:

***The treatment.** See Sections 7.1 and 7.2 of the CIP.

***The population.** See study inclusion and exclusion criteria in Sections 6.3 and 6.4 of the CIP, and the description of the main analysis set populations that will be used in Section 7.2.

***The endpoint.** The final endpoints are defined in Sections 7.9.2 and 7.9.3. When the composite strategy has been used to account for the identified intercurrent events, the intercurrent events have been incorporated into the final endpoint definition, see further information below in Sections 7.9.2 and 7.9.3.

***Other intercurrent events.** In this study, the strategy for addressing intercurrent events has been chosen to be built into one of the other attributes, namely the endpoint attribute, i.e. the composite strategy has been applied to the identified intercurrent events.

***Population-level summary of the endpoint.** This is described in Section 7.9.2 and 7.9.3.

